### 3.2.1. Management of potential confounding factors / bias

Bias will be controlled by strict adherence to the registry protocol. Sites will be monitored for compliance with registry protocol, including subject eligibility criteria, as allowed by EC regulations. In order to minimize selection bias, it is mandatory that the enrollment of patients will be consecutive in nature based on the date of the index procedure. Gore has put in place quality control in order to ensure that no selection bias is applied by the site during patient screening, please see section 5.4 for more details.

The registry is meant to retrospectively collect data for descriptive reporting as well as evaluate "real world" experience of clinical practice and patient outcomes during treatment and throughout follow-up extending up to 2-5 years, by cohort. Patient selection, diagnostic imaging and treatment interventions will be determined by physicians based on this protocol and clinical practice standards.

It is well known that excluding treated patients who are deceased or not reachable at the time of the inclusion due lack of informed consent can generate an important selection bias in retrospective study and is likely to seriously prevent the achievement of the research objectives. Therefore, for patients, who are deceased or not reachable at the time of the inclusion, the consent can be waived, according to national and local regulation. Refer to section 5.2 regarding the waived process.

# 3.3. Registry Endpoint(s)

### 3.3.1. Definitions

Outcome	Definition
Primary Patency	
Aortic Aneurysm / PAD Cohort	Patency of the study graft without additional or secondary surgical or endovascular procedures to maintain or restore flow to the graft. The only exceptions that do not disqualify the graft for primary patency are procedures performed for disease beyond the graft and its two anastomoses.
Dialysis Access Cohort	Interval following intervention until the next access thrombosis or repeated intervention.
Secondary Patency	
Aortic Aneurysm / PAD Cohort	Patency of the study graft with additional or secondary surgical or endovascular procedures to restore flow to the graft after occlusion or stenosis of the graft or its anastomoses  The only exceptions that do not disqualify the graft for secondary patency are procedures performed for disease beyond the graft and its two anastomoses
Dialysis Access Cohort	Patency of the study graft from the time of access creation or placement until access abandonment
Limb Salvage	Freedom from an amputation above the level of the ankle of the index limb
Amputation Free survival	Freedom from an amputation above the level of the ankle of the index limb or all cause death
Device-related seroma or infection PAD Cohort	Clinical evidence of an infectious process in the direct vicinity of the access site or distal to the treated vascular site or seroma classified by the registry investigator as primarily related to the registry device

Device-related infection requiring reoperation PAD Cohort	Clinical evidence of an infectious process in the direct vicinity of the access site or distal to the treated vascular site classified by the registry investigator as primarily related to the registry device and required surgical intervention
Device-related infection  Dialysis Access Cohort	Clinical evidence of an infectious process in the direct vicinity of the access site classified by the study investigator as primarily related to the study device
Survival	All Cause survival
Device-related Adverse Events	Any untoward medical occurrence classified by the registry investigator as primarily related to the registry device

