### 3.3.2. Primary Endpoints

- 3.3.2.1. Peripheral Artery Disease Cohort
  - Primary Safety Outcome: Device-related seroma or infection through 5 years
  - Primary Performance Outcome: Secondary patency (revascularization) through 5 years
- 3.3.2.2. Aortic Aneurysm Cohort
  - Primary Safety Outcome: Survival through 5 years
  - Primary Performance Outcome: Primary patency through 5 years
- 3.3.2.3. Dialysis Access Cohort
  - Primary Safety Outcome: Device-related infection through 2 years
  - Primary Performance Outcome: Useable access circuit (reported as secondary patency) through 2 years

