### 3.3.3. Secondary Endpoints

- 3.3.3.1. Peripheral Artery Disease Cohort
  - Limb Salvage through 1 year
  - Amputation-free survival through 1 year
  - Device-related Adverse Events through 1 year
  - Device-related infection requiring reoperation through 5 years
  - Primary Patency through 1 year
- 3.3.3.2. Dialysis Access Cohort
  - Primary patency through 1 year
  - Device-related adverse events through 1 year

No secondary endpoints have been identified for the Aortic Aneurysm Cohort.

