# 10.2. Sample Size Assumptions

The sample size for the study is estimated using the desired width of the 95% confidence interval. It is assumed that for PAD and Dialysis cohorts, if the estimated percentage of the primary outcome is around 55%, the half-width of the confidence interval would be 12%. Similarly, for the Aortic Aneurysms, considering the primary outcome to be around 32%, the sample size of 65 subjects would allow the half-width of the confidence interval to be lower than 12%.

Cohort	Endpoint Used for Sample Size Calculation, Assumed Rate	Sample Size
PAD	≥ 56% Secondary patency (revascularization) at 5 years	72 Patients (per device)
Aortic Aneurysm	≥ 33% survival at 5 years	65 Patients
Dialysis Access	≥ 55% secondary patency through 2 years	72 Patients (per device)

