# 7.0 Analysis Specifications

SAS Analysis Dataset Specifications

- A specifications document is created following the template defined in MD146539 Work Instructions for Analysis Data Set (ADS) and MD146540 Analysis Data Set (ADS) Template for each analysis data set with at least the following details:
- Variable name
- Format
- Label
- Input variables and derivation rules

Statistical Output Specifications

- A specifications document is created in accordance with the corresponding template that contains at least the following details:
- Title and footnote
- Column headers
- Row labels for tables
- Cell formats
- Datasets and variables used with derivation details
- Revision history

Verification Level for Statistical Output

- All Analysis Datasets Level I
- All Tables Level I
- All Listings Level II

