# 8.0 Data Sets, Tables, Figures, and Listings

This section includes a list of the minimal planned statistical outputs, including tables, listings and figures which are to be created for the regulatory reports defined in the protocol. A different selection of tables, listings, and figures can be created for all other reporting efforts (Annual Reports etc.) as deemed necessary.

- 8.1 Analysis Tables
  - Summary of Subject Demographics by cohort
  - Summary of Medical History by cohort
  - Summary of concomitant medication by cohort
  - Summary of procedural details and assessments by cohort
  - Summary of discharge details by cohort
  - Summary of the devices used by cohort
  - Summary of follow-up, subject availability by visit with counts and percentages.
  - Kaplan-Meier estimate of the Device-related seroma or infection through 5 years in the PAD cohort
  - Kaplan-Meier estimate of the Secondary Patency (revascularization) through 5 years in the PAD cohort
  - Kaplan-Meier estimate of Survival through 5 years in the AA cohort
  - Kaplan-Meier estimate of the Primary Patency through 5 years in the AA cohort
  - Kaplan-Meier estimate of the Device-related infection through 2 years in the DA cohort
  - Kaplan-Meier estimate of the Useable access circuit(reported as secondary patency) through 2 years in the DA cohort
  - Kaplan-Meier estimate of the Limb Salvage through 1 year in the PAD cohort
  - Kaplan-Meier estimate of the Amputation-free survival through 1 year in the PAD cohort
  - Kaplan-Meier estimate of the Device-related Adverse Events through 1 year in the PAD cohort
  - Kaplan-Meier estimate of the Device-related infection requiring reoperation through 5 year in the PAD cohort
  - Kaplan-Meier estimate of the Primary Patency through 1 year in the PAD cohort

- Kaplan-Meier estimate of the Device-related Adverse Events through 1 year in the DA cohort
- Kaplan-Meier estimate of the Primary Patency through 1 year in the DA cohort
- Summary of the Device-related SAEs by cohort
- Summary of the Device-related death by cohort
- Summary of the procedure-related death by cohort
- Summary of the procedure-related SAE by cohort
- Summary of Repeat Interventions by cohort
- Summary of Freedom from Limb Salvage by cohort
- Summary of Device or Procedure Related Serious Adverse Events by cohort
- Summary of Adverse Events by MedDRA SOC, HLT, PT and Follow-up Interval (Number of Subjects, Number of Subjects with AEs, Number of AEs, at Procedure) by cohort

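### The PAD secondary-patency definition contradicts itself: a graft reopened by a procedure on the graft or an anastomosis is both counted as patent and disqualified

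*Protocol*

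**What the plan says.** In Protocol 3.3.1 the aortic/PAD definition of secondary patency has two sentences. The first counts a graft as patent with additional surgical or endovascular "procedures to restore flow to the graft after occlusion or stenosis of the graft or its anastomoses". The second reads: "The only exceptions that do not disqualify the graft for secondary patency are procedures performed for disease beyond the graft and its two anastomoses".

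The primary-patency row of the same table ends with: "The only exceptions that do not disqualify the graft for primary patency are procedures performed for disease beyond the graft and its two anastomoses". The two exception sentences differ by one word.

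SAP Table 1 repeats the definition without comment. The endpoint is listed in Protocol 3.3.2.1 as "Primary Performance Outcome: Secondary patency (revascularization) through 5 years" and in SAP 8.1 as "Kaplan-Meier estimate of the Secondary Patency (revascularization) through 5 years in the PAD cohort". Protocol 10.2 and SAP Table 2 base the PAD sample size on it, with an assumed rate of at least 56% and 72 patients per device. PAD primary patency is a separate secondary endpoint, "Primary Patency through 1 year" (Protocol 3.3.3.1). SAP 7.0 leaves "Input variables and derivation rules" to a separate specification document.

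**The concern.** The exception clause makes sense under primary patency, where any procedure on the graft or an anastomosis should end patency. Under secondary patency it removes the cases that the endpoint exists to count. The near-identical wording suggests that the sentence was carried over from the row above.

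A programmer or site applying the written words can reach either classification for the same graft. Under the second sentence, the PAD primary performance endpoint becomes in effect primary patency at 5 years, and the result can no longer be set against the assumed 56%. A choice between the readings made once outcomes are known could also look data-driven. No core laboratory (Protocol 6.4) or clinical event committee (SAP 4.1) is planned that would impose one reading.

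**Working it through.** **1. The two sentences side by side**

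| Situation of the graft | Sentence 1 | Sentence 2 |
|---|---|---|
| Occluded or stenosed, reopened by a procedure on the graft or an anastomosis, then patent | Patent | Disqualified |
| Procedure only for disease beyond the graft and anastomoses, graft patent | Not addressed | Not disqualified |
| Occluded, flow not restored | Not patent | Not patent |

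The conflict lies in the first row. The second sentence allows only one class of procedure, so the two cannot be combined.

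**2. Scope**

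The row covers the aortic cohort too, but that cohort's performance endpoint is primary patency and it has no secondary endpoints (Protocol 3.3.2.2 and 3.3.3). Dialysis secondary patency has its own definition, which runs to access abandonment. The damage is therefore confined to the PAD endpoint, which is analysed in two of the five analysis populations (Protocol 10.6.2).

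**3. The plan's own figure**

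Inputs from Protocol 10.2 and 10.3 and SAP 5.0: two-sided exact binomial 95% interval, target half-width 12 points, rate 55% to 56%. The Clopper-Pearson limits for x patent grafts out of n are

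- lower = 0.025 quantile of Beta(x, n − x + 1)
- upper = 0.975 quantile of Beta(x + 1, n − x)

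With n = 72 and x = np, the half-width is 11.97 points at 55% and 11.94 points at 56%. At both rates 72 is the smallest n with a half-width of 12 points or less, so the stated sample size reproduces.

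**4. Illustration of the effect on the estimate**

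Let r be the share of all grafts that are patent only because of a procedure on the graft or an anastomosis. The documents give no value; 5% to 20% is assumed. If 56% is the rate under sentence 1, the rate under sentence 2 is 0.56 − r:

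- r = 0.05: 0.51
- r = 0.10: 0.46
- r = 0.20: 0.36

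These values of r are 9%, 18% and 36% of the grafts counted as patent under sentence 1 (r / 0.56).

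In whole patients, starting from 40 of 72 patent under sentence 1:

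| Rescued grafts | Share of 72 | Scored patent | Estimate | Exact 95% CI | Half-width (points) |
|---|---|---|---|---|---|
| counted as patent | – | 40 | 55.6% | 43.4 to 67.3 | 11.96 |
| 4 scored as failures | 5.6% | 36 | 50.0% | 38.0 to 62.0 | 12.02 |
| 7 scored as failures | 9.7% | 33 | 45.8% | 34.0 to 58.0 | 11.99 |
| 14 scored as failures | 19.4% | 26 | 36.1% | 25.1 to 48.3 | 11.59 |

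The estimate moves by 5.6 to 19.4 points while the half-width stays between 11.6 and 12.0. Meeting the precision target therefore gives no sign of which reading was used.

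**The case against.** The strongest reply is that the intent is plain. The endpoint carries the label revascularization, primary patency has its own definition and its own PAD endpoint, and the second sentence would leave the first almost without content. Nothing in the documents shows that anyone plans to code the exception clause literally. The analysis is descriptive (Protocol 10.1), and reintervention dates and procedural data are recorded (Protocol 5.9), so the classification could be corrected at derivation. The dataset specification, or the definitions list cited in SAP 9.0, may already settle the rule. The 5% to 20% range has no source in the documents.

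Much of this stands. Context does favour the first sentence, the size of the effect is hypothetical, and the harm arises only if the clause is applied. But an inferable intent shows what the correction should be; it does not make the text usable. The protocol and SAP are the governing documents, both carry the contradiction, and neither refers the reader elsewhere for a ruling on it. A primary endpoint should not depend on the programmer's inference.

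**Conclusion.** The concern holds. As written, the PAD primary performance endpoint has two incompatible definitions, and the clause stated as exclusive is the one that does not fit the endpoint's label. Applying it can only lower the estimate, by the share of grafts kept patent through procedures on the graft or an anastomosis. Under the assumed 5% to 20%, an expected 56% becomes 51% to 36%; the true share cannot be obtained from the documents. The contradiction itself does not depend on that assumption. The sample size of 72 per device stands, and because no test is planned there is no wrong test decision. What is at risk is a primary estimate that does not measure the quantity it is named for. It must be corrected before outcomes are derived.

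**What to change.** In Protocol 3.3.1 and SAP Table 1, delete the exception sentence from the aortic/PAD secondary-patency row. State instead that:

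- a graft is secondarily patent if it is patent at the time point, with or without procedures on the graft or its anastomoses (the present first sentence says only *with*, so read literally it omits grafts that never needed a procedure);
- procedures for disease beyond the graft and anastomoses do not affect the classification, so nothing useful is lost with the deleted sentence;
- secondary patency is lost at an occlusion in which flow is not restored.

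Put the same rule into the dataset derivation specification named in SAP 7.0.

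Two related points can be settled at the same time. First, state whether explant or graft replacement is analysed as loss of patency or as censoring, consistently with Protocol 5.13.1 and the SAP 4.0 text on discontinuation. Second, check that the CRF allows an unrestored occlusion to be dated: reintervention dates and adverse-event onset dates are collected (Protocol 5.9 and 9.1.3), but the list in Protocol 5.8.2 names no separate occlusion date.

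The cost is a wording change in two tables and one derivation rule. No change to the sample size is needed.

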### 4.2.2. PAD Cohort Inclusion Criteria

1. Patient was treated for peripheral arterial disease or peripheral arterial aneurysm requiring bypass treated

Vascular Graft at least 5 years before site initiation.

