### 4.2.4. Dialysis Access Cohort Inclusion Criteria

### 4.3. Exclusion Criteria

### 4.3.1. General Exclusion Criteria

- 1. Patient was not available for follow up (on-site or remotely) at the clinical site, with the exception of death (e.g., patient lost to follow-up immediately after treatment, patients who live far away from the clinical site and are not available to share follow-up data performed locally).
- 2. At the time of treatment, patient had known coagulation disorders, including hypercoagulability, that were not amenable to treatment.
- 3. Patient was pregnant at the time of treatment.
- 4. Patient had known or suspected systemic infection or infection at the site of graft implantation at the time of implant.
- 5. Patient had a separate major interventional or surgical vascular procedure within 30 days prior to treatment. CVC catheter placement would be permitted.
- 6. Patient is already enrolled in this registry under a different cohort.

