#### **Table 1. Protocol Definitions**

Outcome	Definition
Primary Patency	
Aortic Aneurysm / PAD Cohort	Patency of the study graft without additional or secondary surgical or endovascular procedures to maintain or restore flow to the graft. The only exceptions that do not disqualify the graft for primary patency are procedures performed for disease beyond the graft and its two anastomoses.
Dialysis Access Cohort	Interval following intervention until the next access thrombosis or repeated intervention.
Secondary Patency	
Aortic Aneurysm / PAD Cohort	Patency of the study graft with additional or secondary surgical or endovascular procedures to restore flow to the graft after occlusion or stenosis of the graft or its anastomoses

	The only exceptions that do not disqualify the graft for secondary patency are procedures performed for disease beyond the graft and its two anastomoses
Dialysis Access Cohort	Patency of the study graft from the time of access creation or placement until access abandonment
Limb Salvage	Freedom from an amputation above the level of the ankle of the index limb
Amputation Free survival	Freedom from an amputation above the level of the ankle of the index limb or all cause death
Device-related seroma or infection PAD Cohort	Clinical evidence of an infectious process in the direct vicinity of the access site or distal to the treated vascular site or seroma classified by the registry investigator as primarily related to the registry device
Device-related infection requiring reoperation PAD Cohort	Clinical evidence of an infectious process in the direct vicinity of the access site or distal to the treated vascular site classified by the registry investigator as primarily related to the registry device and required surgical intervention
Device-related infection Dialysis Access Cohort	Clinical evidence of an infectious process in the direct vicinity of the access site classified by the study investigator as primarily related to the study device
Survival	All Cause survival
Device-related Adverse Events	Any untoward medical occurrence classified by the registry investigator as primarily related to the registry device

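### The PAD infection definitions rest on an 'access site' that is not defined for a bypass, so infection along the graft body or tunnel can be missed or counted differently between sites

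*Protocol*

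**What the plan says.** Protocol 3.3.2.1 sets the PAD endpoint as "Primary Safety Outcome: Device-related seroma or infection through 5 years". The definitions table in protocol 3.3.1 says what qualifies. An infection counts when it is found "in the direct vicinity of the access site or distal to the treated vascular site or seroma"; the site investigator must also judge the event primarily device-related. SAP Table 1 carries the same text, "in the direct vicinity of the access site or distal to the treated vascular site or seroma classified by the registry investigator", and adds no explanation.

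The secondary outcome of device-related infection requiring reoperation, also through 5 years, has the same two locations and ends "distal to the treated vascular site classified by the registry investigator as primarily related to the registry device and required surgical intervention".

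The index procedure is a bypass. Protocol 4.2.2 reads "Patient was treated for peripheral arterial disease or peripheral arterial aneurysm requiring bypass treated" with the study graft. Neither document defines the access site for such a procedure. Neither names the graft body, tunnel or anastomoses as a qualifying place for infection.

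SAP 4.1 states that a clinical event committee is not applicable. Protocol 3.2.1 relies on strict adherence to the protocol to control bias.

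**The concern.** The location text is a counting rule for a primary safety outcome in 144 patients (72 per device). It works only if every site reads it the same way, and its key term is open. An investigator who takes the access site to be the incision or incisions will find no place in the definition for an infection midway along the graft or in its tunnel. One who takes it to be the operative field will count that infection. Both follow the text.

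At stake is what the reported rate means. The analysis is descriptive (protocol 10.1), so the estimate and its interval are the result. If the literal reading prevails, device infection is under-stated. If readings differ, the pooled figure mixes two definitions across up to 9 sites. The other 5-year PAD infection outcome shares the location limit, so it cannot serve as a check.

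**Working it through.** **1. The plan's own figure.** Inputs: n = 72 per device, exact binomial 95% interval, half-width 12%, secondary patency of about 55% to 56% (protocol 10.2; SAP 2.6 and Table 2). The exact limits for x events in n are

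- lower = 2.5% quantile of Beta(x, n − x + 1)
- upper = 97.5% quantile of Beta(x + 1, n − x)

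With x = np:

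- p = 0.55: limits 0.4282 and 0.6676, half-width (0.6676 − 0.4282)/2 = 0.1197
- p = 0.56: limits 0.4380 and 0.6769, half-width (0.6769 − 0.4380)/2 = 0.1194

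In both cases 72 is the smallest n with a half-width of at most 0.12, so the figure reproduces. It rests on secondary patency. The infection definition does not enter it.

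**2. The wording side by side.**

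| Place | How location is described | Fit |
|---|---|---|
| PAD primary safety definition (protocol 3.3.1, SAP Table 1) | access site, or distal to the treated site | access site undefined for a bypass |
| PAD infection requiring reoperation (same tables) | same two zones | same gap |
| Dialysis infection definition (same tables) | access site only | fits: the graft is the vascular access |
| PAD and aortic patency definitions (same tables) | the graft and its two anastomoses | names the graft |
| General exclusion 4 (protocol 4.3.1) | site of graft implantation | names the implant site |

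The dialysis entry begins "Clinical evidence of an infectious process in the direct vicinity of the access site classified by the study investigator as primarily related to the study" and uses the same phrase where its meaning is plain. General exclusion 4 uses "infection at the site of graft implantation at the time of implant". Graft-based wording was thus available within the protocol, but the PAD infection definitions do not use it.

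**3. Which events are in doubt.** The ends of the graft and the anastomoses are reached through the surgical exposures, so even a narrow reading can include them. The doubtful region is the graft body between them and its tunnel. Seroma can be read as having no location limit, so the gap concerns infection only.

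**4. Where a doubtful event would still appear.**

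- Device-related adverse events: no location limit, but this endpoint stops at 1 year (protocol 3.3.3.1).
- Infection requiring reoperation: 5 years, but the same location limit.
- SAP 8.1 and 8.2: summaries of device-related serious adverse events, repeat interventions and all adverse events, plus an adverse event listing. No 1-year limit is stated for these.

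An infection along the graft body or tunnel after year 1 could therefore be absent from every PAD infection endpoint while remaining in the general safety tables.

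**5. Illustration of size.** The documents give neither an infection rate nor the share along the graft. The counts below are assumptions, with n = 72, every patient evaluable, and the exact interval named in SAP 5.0.

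| Device infections assumed | All counted (broad reading) | Half not counted | None counted |
|---|---|---|---|
| 2 | 2.8% (0.3 to 9.7) | 1.4% (0.0 to 7.5) | 0% (0 to 5.0) |
| 4 | 5.6% (1.5 to 13.6) | 2.8% (0.3 to 9.7) | 0% (0 to 5.0) |
| 6 | 8.3% (3.1 to 17.3) | 4.2% (0.9 to 11.7) | 0% (0 to 5.0) |
| 8 | 11.1% (4.9 to 20.7) | 5.6% (1.5 to 13.6) | 0% (0 to 5.0) |

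The effect runs from nothing to the whole estimate, depending on the reading and on where the infections lie.

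**The case against.** The strongest reply is that no exclusion has been shown. The term is undefined, a bypass is an open operation, and an investigator may reasonably take the access site to be the operative field. In the dialysis cohort the same phrase does take in the graft. This stands. A reader might infer that graft infection definitely falls outside the definition; the documents do not support that. They support only that it falls outside on one legitimate reading and inside on another.

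A second reply is that location may never act as a filter. The adverse event fields listed in protocol 9.1.3 include name, dates, relationship and seriousness, but no anatomical site. An endpoint built from event term and relationship would pick up a graft infection. That is possible, but the case report form is not in the documents, and an endpoint built that way would depart from its written definition.

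A third reply is that the investigator's attribution to the device does the real selecting. It does restrict what counts, and it means that a distal infection not attributed to the device is not counted. But it is a further condition on top of location and cannot bring in a location that the text leaves out.

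A fourth reply is that the events are reported elsewhere. This also stands, as set out in the working. It limits the harm to the endpoint estimates.

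**Conclusion.** The point holds as an ambiguity in a counting rule. Both PAD infection definitions turn on a term with no stated meaning for a bypass, and the two natural readings treat graft-body and tunnel infection in opposite ways. Both 5-year PAD infection outcomes can therefore under-count such infections or count them differently between sites, and nothing in the plan reconciles the readings.

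The size is unknown. The illustrations rest on assumed event counts and assumed shares and are not estimates of what this registry will see.

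Two further inferences should be resisted. One is that graft infections would go unreported: adverse events are to be reported from the index procedure to completion or discontinuation, and the general tables would show them. The other is that the distal category is misplaced and should go: nothing in the documents supports removing it, and doing so could lower the count of a safety outcome.

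**What to change.** In both PAD infection definitions, in protocol 3.3.1 and in SAP Table 1 (four places), replace the reference to the access site with: in the direct vicinity of the study graft (graft body, tunnel or anastomoses) or of the surgical incisions used to implant it. Keep the category for infection distal to the treated vascular site, and keep the requirement that the investigator judge the event primarily device-related. Distal events may be tabulated separately if that helps interpretation. Add one line of site guidance so that all sites apply the same text.

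The cost is a wording amendment, with the ethics committee approval that protocol 6.6 requires. Events already entered would need to be re-read against the new text, which may mean returning to the chart because no anatomical field is listed. The observed infection rate may rise slightly. The sample size of 72 per device does not change, because it rests on secondary patency.
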